Unsolicited AE recording ^h		----- continuous -----											●
SAE recording		----- continuous -----											●
Concomitant medications ^s		----- continuous -----											●
Challenge virus inoculation							●						
Nasal wash sample ⁱ					●				⑥	●			
RVAT (from nasopharyngeal swab) ^c										●			
Subject symptom card					●	⑦	⑦	⑦	⑦	●			
Spirometry	●				●	●	●	●	●	●			
24-hour tissue count and mucus weight					●	●	●	●	●	●			
Approx daily blood draw, mL	10	70	–	10	70	–	–	30	10	70	–	70	
Approx cumulative study blood draw, mL	10	80	80	90	160	160	160	190	200	270	270	–	

AE = adverse event; d = day; chall = challenge; ECG = electrocardiogram; HIV = human immunodeficiency virus; ICF = informed consent form; mo = month; RVAT = rapid virus antigen test; SAE = serious adverse event; vacc = vaccination

① pre-dose; ② pre- and post-dose; ③ screening laboratory tests are to be done within 56 days of randomization; ④ blood samples for immunogenicity will only be taken if the early exit is ≥14 days after the previous immunogenicity blood draw; ⑤ if within 7 days of study vaccination; ⑥ check of diary during the telephone call; ⑦ three times daily; ⑧ every 12 (±1) hours; ⑨ on Days 3, 7 and 11; ⑩ Days 3, 7, and 11 for cardiac enzymes only. Note: cardiac enzymes will also be assessed on entry to the quarantine Unit in addition to biochemistry and hematology parameters.

- a. Intranasal challenge with the RSV-A Memphis 37b virus will occur on Day 0, not less than 24 or more than 90 days after vaccination.
- b. At 48-hours post-vaccination, a telephone call will additionally be made to two sentinel subjects to collect safety information.
- c. Subjects will only be discharged if no detectable virus is present (negative RVAT) in nasopharyngeal samples taken on Day 12. If symptoms are present, but no virus is detected (negative RVAT), discharge will be at the investigator’s discretion. If appropriate, subjects may reside in quarantine for an additional night or longer before discharge.
- d. Historical pre-screening data collected through the ethics committee-approved hVIVO screening protocol within 56 days (90 days for viral serology) to 3 days prior to vaccination may be used for screening procedures. Historical pre-screening data obtained prior to this window can be re-assessed any time from 40 days to 3 days prior to vaccination.

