9.1.5. Viral Challenge Phase

9.1.5.1. Entry to the Quarantine Unit

Subjects will enter the quarantine Unit either one or two days before the viral challenge, to acclimatize and perform entry assessments. The following assessments can take place on either day: complete physical examination, including body weight, relevant medical information since vaccination, vital signs and spirometry, samples for clinical laboratory tests (including cardiac enzymes), ECG, blood samples for immunogenicity assessments, spirometry, and recording of any unsolicited AEs/SAEs and concomitant medications. Nasopharyngeal swabs and nasal wash samples will be collected to screen for respiratory virus and for RSV pre-F antibody assessment, respectively, and blood samples will be taken to determine sero-susceptibility for RSV for post-hoc reconfirmation (neutralization assay).

The SSC will be filled out by the subject and reviewed by the attending physician. Tissues for tissue counts and mucus weight will be distributed on Day -1. The first 24-hour collection will start on Day -1; tissue counts and mucus weights will be determined on Day 0.

A serum pregnancy test (β -hCG) will be performed for all female subjects. A urine drug screen, a urine cotinine test, and an alcohol breath test will be performed.

Throughout the challenge phase of the study from entry to the Unit until discharge, subjects will stay in individual isolation rooms to minimize cross-contamination between subjects.

Before challenge inoculation on Day 0, the subject's clinical status will be checked, including any available laboratory results or receipt of additional medical records.

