9.2.6.2. Clinical Laboratory Tests

Blood and urine samples for laboratory safety assessments will be collected for screening up to 56 days prior to vaccination, pre-vaccination, 7 days post-vaccination, and prior to challenge on Day -1 or Day -2. Blood samples will additionally be collected at discharge from the quarantine Unit and at 28 days post-challenge. The following tests will be performed by a local laboratory (*parameters only measured at screening):

- **Hematology Panel**

- platelet count.
- white blood cell (WBC) count (absolute)
- WBC differential
 - neutrophils
 - lymphocyte
 - monocytes
 - eosinophils
 - basophils
- red blood cell (RBC) count
- reticulocyte count (% and absolute)
- hemoglobin
- hematocrit
- mean corpuscular volume (MCV)
- mean corpuscular hemoglobin (MCH)
- MCH concentration (MCHC)

- **Biochemistry Panel**

- sodium
- potassium
- glucose (random)
- albumin

chloride
bicarbonate
calcium
uric acid
total protein
creatinine
total, direct, and indirect bilirubin
inorganic phosphate
blood urea nitrogen
C-reactive protein
gamma glutamyl transferase
alkaline phosphatase
alanine transaminase
lactate dehydrogenase
aspartate transaminase
urea

- **Cardiac Enzymes** (done together with ECGs on admission, and on Days 3, 7 and 11)

Troponin T
creatinine kinase

- **Urinalysis** – dipstick for:

specific gravity
pH
glucose
protein
blood
ketones
appearance
color
nitrite
urobilinogen
bilirubin
leucocytes

A repeat urinalysis will be performed in the event of a positive dipstick test. Microscopic reflex testing will be carried out if the repeat urinalysis dipstick test is also positive.

Review and Grading of Laboratory Data

The investigator must review each laboratory result, document this review and assess systematically any clinical significance. The laboratory reports must be filed with the source documents.

Laboratory values will be initially evaluated by the investigator according to local laboratory criteria. Abnormal values outside the local laboratory range of normal will be graded according to the FDA Guidance document “Toxicity Grading Scale from Healthy Adult and Adolescent Volunteers Enrolled in Preventive Vaccine Clinical Trials” (see [Attachment 1](#)). Laboratory values within local laboratory normal limits will not be FDA graded and will be considered as normal.

Reporting Laboratory Abnormalities as AEs

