3. GENERAL ANALYSIS DEFINITIONS

3.1. Study phases

The baseline (or reference) value for safety and immunogenicity analysis will be defined as the value of the last available assessment prior to vaccination (Day -28). For ECG values the baseline (or reference) value will be defined as the value of the last available assessment prior to challenge on Day 0, since ECGs for safety assessment are performed only during the challenge period.

The baseline (or reference) value for the efficacy analysis will be defined as the value of the last available assessment prior to challenge on Day 0.

The safety analysis will present all results by period, based on the phase definition in Section [3.1.1](#).

The immunogenicity analysis will summarize all results in the following immunogenicity timepoints:

- Baseline (vaccination)
- 28 days post-vaccination*
- 28 days post-challenge

*Includes all assessments taken between 22 and 33 days after vaccination.

In case there are subjects for which samples were taken later than 33 days after vaccination, the results will appear in listings.

Moreover,

$$\text{Study Day} = \text{visit date} - \text{date of Vaccination}$$

Listings will be shown per phase and time point.

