7.2. Clinical Laboratory Tests

For laboratory safety parameters, only abnormalities emerging will be tabulated by worst abnormality grade using the FDA table in [Attachment 1](#). Blood and urine for laboratory safety assessments will be collected within 56 days of vaccination, pre-vaccination, at 7 days post vaccination, prior to challenge on Day -1 or Day -2, post challenge at day 12 and Day 28. Moreover, blood for assessment of cardiac enzymes will also be collected on Days 3, 7, and 11.

An abnormality (toxicity grade or abnormality based on normal ranges) will be considered as emerging in a particular period if it is worse than the baseline value. If the baseline is missing, the abnormality is always considered emerging. A shift from ‘abnormally low’ at baseline to ‘abnormally high’ post baseline (or vice versa) is also emerging. In case a laboratory test result is censored (no numeric value is available, but only a verbatim term) then a numeric value will be imputed by a value exceeding the cut-off value with one unit. (<x: subtract 1 unit from x, >x: add 1 unit to x; <3.45 is imputed with 3.44).

In case no toxicity grades are defined for a test, the abnormalities (above/below normal range) will be used. In determining toxicity grades, the following rules are applied:

- worst grades/abnormalities are determined over the whole observational period for each trial period separately, including all post-baseline measurements of that period.
- The abnormalities ‘abnormally low’ and ‘abnormally high’ are considered equally important, i.e. if a subject has as well an abnormally low as an abnormally high value post-baseline, both abnormalities are shown in the tables. (This means that the sum of the percentages can be more than 100%)
- Note: as the grading scale for some parameters in the grading table has some gaps (zones where no toxicity grade definition exists), laboratory results falling in these zones will be allocated to the adjacent worst-case grade.
- If a laboratory value falls within the grading as specified in the grading table but also within the local lab normal limits, the value is considered as normal.
- HGB: for hemoglobin grades are based on both actual values and changes. Those grading will be listed separately. In addition, for the grading on the changes of HGB, the corresponding actual value should be at least grade 1.

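### Troponin T and creatine kinase have no pre-vaccination sample, so the SAP's missing-baseline default classes every abnormal value as emerging, including post-challenge values no worse than at admission

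*SAP*

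**What the plan says.** SAP 3.1 defines the reference for safety data, which it ties to Day -28: "The baseline (or reference) value for safety and immunogenicity analysis will be defined as the value of the last available assessment prior to vaccination". It makes one safety exception. ECGs take the last assessment before challenge, "since ECGs for safety assessment are performed only during the challenge period".

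SAP 7.2 tabulates only emerging laboratory abnormalities, by worst grade and separately for each period. An abnormality "will be considered as emerging in a particular period if it is worse than the baseline value". The next sentence covers the other case: "If the baseline is missing, the abnormality is always considered emerging". Tests without a toxicity grade are handled by normal range under the same rule.

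Protocol 9.2.6.2 lists troponin T and CK under their own heading, "done together with ECGs on admission, and on Days 3, 7 and 11". The notes to the Time and Events Schedule agree: "cardiac enzymes will also be assessed on entry to the quarantine Unit in addition to biochemistry and hematology parameters". Neither enzyme is in the hematology or biochemistry panels of Protocol 9.2.6.2, and Protocol 9.1.3 (screening) and 9.1.4.1 (vaccination) do not mention them.

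**The concern.** A missing-baseline default is normally a cautious way of treating the occasional lost sample. Here it governs both enzymes in every subject, because the schedule provides no sample that could serve as baseline. The post-challenge table therefore cannot separate an enzyme that rose after inoculation from one that was already raised on arrival at the Unit.

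This matters because Protocol 1.3.4 names myocarditis as a possible effect of the challenge virus, and these are the laboratory tests most directly relevant to it. A reader of the clinical study report would reasonably take an emerging post-challenge enzyme abnormality to be one that was absent, or milder, before inoculation. Under the current rule it need not be.

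**Working it through.** The plan states no figure to reproduce. The check applies the SAP rules to the protocol's sampling schedule.

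**Step 1. Samples eligible as baseline.** Scheduled enzyme samples are admission (Day -2 or -1), Day 3, Day 7 and Day 11, four in all (Protocol 9.2.6.2, 9.1.5.1 and 9.1.5.3). Scheduled before vaccination: 0 of 4. Scheduled before challenge: 1 of 4. Under SAP 3.1 as written, the baseline is missing for every subject unless an unscheduled or historical result happens to exist; none is planned.

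**Step 2. Period of each sample (SAP Table 2).** On the target schedule challenge is 28 days after vaccination, so admission falls at 28 − 2 = 26 or 28 − 1 = 27 days. That is before challenge and within the 32-day limit of the Post-Dose period. For overflow subjects admitted more than 32 days after vaccination, the admission value falls in the Follow-up Vaccination phase. Days 3, 7 and 11 are always in Post-Challenge.

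**Step 3. Classification in the Post-Challenge period.**

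| At admission | Worst value on Days 3, 7, 11 | SAP as written | With pre-challenge baseline |
|---|---|---|---|
| Normal | Abnormal | Emerging | Emerging |
| Abnormal | Abnormal, worse grade | Emerging | Emerging |
| Abnormal | Abnormal, same grade | Emerging | Not emerging |
| Abnormal | Abnormal, milder grade | Emerging | Not emerging |
| Abnormal | Normal | Not emerging | Not emerging |

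The third and fourth rows are the error: the abnormality preceded inoculation and did not worsen. On the target schedule the same subjects also appear as emerging in Post-Dose, where there is again no baseline.

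**Step 4. Grading.** CK is graded in SAP Attachment 1 (as CPK, Grade 1 from 1.25 × ULN). Troponin T is not in that table, so it is only inside or outside the normal range. The missing-baseline default reaches both.

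**Step 5. Comparison with ECGs.** ECGs have a screening recording (Protocol 9.2.6.3), yet the SAP still moves their reference to before challenge because the safety ECGs belong to the challenge period. The enzymes are drawn with those same ECGs and have no screening sample at all, so the SAP's reason applies to them at least as strongly.

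**The case against.** The case for leaving this alone has substance. Safety is descriptive, with no formal group comparisons (Protocol 11.7, SAP 7), in an exploratory study of about 44 challenged subjects. The rule treats both arms alike, so it does not by itself tilt the vaccine-placebo contrast. It over-reports rather than conceals. Data are shown by period, so an abnormal admission value is not merged with Days 3 to 11, and SAP 3.1 provides for listings by phase and time point from which individual cases could be traced. All of this stands and limits the severity. It does not make the Post-Challenge entry correct.

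Stronger readings are tempting, and the documents do not support them:

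- **That cardiac safety monitoring is compromised, or that the data cannot show what the challenge did.** The investigator reviews every laboratory result (Protocol 9.2.6.2), available results are checked before inoculation (9.1.5.1), and AEs from admission onward are assessed for relationship to challenge (12.1.2). The laboratory pausing rule in 11.10 rests on persistent Grade 3 or 4 abnormalities judged related to study vaccine. None of these uses the SAP's emerging flag.
- **That every subject's result is wrong.** The baseline is missing for all, but only subjects whose enzyme is abnormal both at admission and after challenge, without worsening, are misclassified.
- **That a count can be given.** The documents give no rate of raised CK or troponin T at admission. The 2 subjects in over 500 in Protocol 1.3.4 had changes suggestive of myocardial inflammation, which is not the same event as an enzyme above range.
- **That the same fault affects all laboratory tests.** Hematology and biochemistry have real pre-vaccination values. Judging a persisting abnormality against them in a later period is a stated convention.

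**Conclusion.** The rule as written gives a wrong classification for these two tests. An enzyme abnormality present at admission and no worse on Days 3 to 11 will be tabulated as emerging after challenge. The conclusion rests on the scheduled samples alone; an unscheduled or historical pre-vaccination enzyme result would supply a baseline for that individual.

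The consequence is limited to the descriptive post-challenge cardiac-enzyme table. Efficacy results, pausing rules, individual clinical monitoring and the baseline convention for other laboratory tests are unaffected. How many of the roughly 44 challenged subjects are involved cannot be derived from the documents and could be none. Severity is minor to moderate. The change is worth making before the analysis because it is cheap and the SAP already accepts the reasoning for ECGs.

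**What to change.** In SAP 3.1, extend the ECG exception: for troponin T and CK, the reference for the Post-Challenge period is the last available value before challenge on Day 0, which is the admission sample.

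That sample is also the only scheduled enzyme measurement between vaccination and challenge, so using it only as a reference would drop abnormal admission values from the tables. Add to SAP 7.2 that these values are reported separately by arm, as pre-challenge findings, and are not classed as emerging. For those subjects, show the Day 3, 7 and 11 values alongside. This also covers troponin T, which has no grades, so a further rise from an already abnormal admission value may not register as a worse category.

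Leave the pre-vaccination baseline for all other laboratory tests as it is. The cost is one sentence in SAP 3.1, one in SAP 7.2, a derivation change and a small table or listing. The admission samples are already scheduled, so no procedure, visit or blood volume changes.

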7.3. Vital Signs and Physical Examination Findings

Similar to laboratory tests, only vital signs abnormalities emerging after vaccination and after challenge will be tabulated by worst abnormality grade.

Heart rate (beats per minutes, bpm), respiratory rate (breaths per minute), systolic blood pressure (mmHg) and diastolic blood pressure (mmHg) will be collected. The respective vital signs abnormalities are defined in Table 4. Moreover, only the vital signs values will be used, no clinical interpretations, therefore, grade 3 and 4 is shown combined as grade 4 always requires clinical interpretation.

Table 4: Vital Signs Toxicity

Vital Signs	Grade 1	Grade 2	Grade 3/4
Tachycardia – beats (HR) per minute	101 – 115	116 – 130	>130
Bradycardia – beats (HR) per minute	50 – 54	45 – 49	< 45
Hypertension (systolic) - mm Hg	141 – 150	151 – 155	>155
Hypertension (diastolic) - mm Hg	91 – 95	96 – 100	>100
Hypotension (systolic) - mm Hg	85 – 89	80 – 84	< 80
Respiratory Rate - breaths per minute	17-20	21-25	>25

Temperature from diary and on-site assessments from day of vaccination will be allocated to predefined temperature intervals (from 37.5° C until 40°C, in steps of half degree increments; eg <37.5, 37.5-<38, 38-<38.5, ... >40). A table will be created, showing the maximum temperature for both diary and onsite assessments combined.

A listing of temperatures from Day -2 or -1 will also be provided.

Temperature collected during the post challenge period will be summarized descriptively over each timepoint.

Finally, a listing of subjects with fever according to the FDA grading table, across the entire study period, will be provided.

Any abnormal physical examination result will be documented as AEs, by the investigator.

7.4. Electrocardiograms

ECGs will be carried on Days -2 or -1, 3, 7 and 11 for safety assessment.

The following measurements will be analysed:

- HR (bpm)
- PR (ms)
- QRS (ms)
- Uncorrected QT (ms)

QT values will be corrected for RR, even if provided in the DB. The following QT correction methods will be used (rounded to the integer value):

$$QT_{cB}(ms) = QT(ms) \times \sqrt{\frac{1000}{RR(ms)}} : \text{Bazett's square - root corrected QT}$$

$$QT_{cF}(ms) = QT(ms) \times \sqrt[3]{\frac{1000}{RR(ms)}} : \text{Fridericia's cube - root corrected QT}$$

If RR is missing, but HR is available from the same ECG reading, the following replacement will be made in the above formulas.

$$\frac{1000}{RR(ms)} = \frac{HR(bpm)}{60}$$

If HR is missing, it will be calculated using RR (if available) and rounded to the integer value (see formula above). HR from the vital signs section (i.e. pulse) will not be used in this ECG analysis section.

Any rounding will be performed after computation of the applicable parameters, and before any further handling.

Abnormalities for the Actual Values

The actual values for HR, PR, QRS and QTc will be categorized into abnormalities using the boundaries defined in the following table (Limits in this table overrule those presented in the protocol.):

Abnormality Codes	HR	PR	QRS	QTcorrected
“abnormally low”		NAP	NAP	
“abnormally high”		≥ 210 bpm	≥ 120 ms	
“abnormally low Grade 1”	[50-54]			
“abnormally low Grade 2”	[45-49]			
“abnormally low Grade 3”	<45 bpm			
“abnormally high Grade 1”	[101,115]			
“abnormally high Grade 2”	[116,130]			
“abnormally high Grade 3”	>130			
“]450 ms, 480 ms]”				$450 \text{ ms} < QTc \leq 480$ ms
“]480 ms, 500 ms]”				$480 \text{ ms} < QTc \leq 500$ ms
“More than 500 ms”				$QTc > 500$ ms

- No abnormalities will be defined for actual uncorrected QT values.
- Uncorrected QT ≥ 500 ms will be flagged and only shown in listings.

Abnormalities on the Changes from Reference (QTc Parameters)

Abnormalities on the change from reference will only be defined for corrected QT, as follows:

1. < 30 ms
2. [30; 60] ms
3. > 60 ms

Only increases by ≥ 30 ms will be considered as abnormalities.

Note: The QTc definitions for abnormalities follow the ICH E14 guidance.

Parameters to Analyze

- actual values: HR, PR, QRS, QT and QTc
- abnormality classifications for the actual values: HR, PR, QRS, QTc
- abnormality classification for the increases from reference: QTc
- worst emergent abnormalities: HR, PR, QRS, QTc, QTc change

Percentages will be calculated relative to the total number of subjects with data.

Note: RR values will only be listed, as well as any original QTc parameter, if provided in the DB. Recalculated HR values will be flagged.

In Case of Missing Date or Time Parts

ECG records with missing assessment date- or time-parts (any: day, month or year) will not be used for descriptive statistics, unless the scheduled target day or time is known and a unique study day allocation is possible taking this additional information into account. These assessments will be allocated to the right study day using the available date (time) information, and the information on their assessment schedule. In case it is not possible to assign a study day to those measurements they will only appear in a listing, including a flag.

Emergent Definition for Abnormalities

Abnormalities defined on actual values: the abnormality worsened as compared to the abnormality at reference; this also includes the shift from ‘abnormally high’ to ‘abnormally low’ and vice-versa. Post-reference abnormalities are always treatment-emergent with regard to missing abnormalities at reference. The abnormalities ‘abnormally high’ and ‘abnormally low’ are considered equally important.

Abnormalities on changes from reference are always defined as emergent (QTc).

8. IMMUNOGENICITY

The analysis of immunogenicity will use the PPI set.

8.1. Exploratory Parameters

The following humoral and cellular immune responses may be measured as part of the evaluation of exploratory objectives, if available:

Immunogenicity against the insert:

Humoral immune response

- RSV neutralization RSV-A Memphis 37b
- Intranasal pre-F antibody, from nasal wash samples.
- RSV F protein enzyme-linked immunosorbent assay (ELISA; pre- and/or post-fusion F antibodies).
- RSV G/N ELISA
- RSV neutralization A strain (titers of neutralizing antibodies).
- RSV neutralization B and/ or a different A strain (titers of neutralizing antibodies),
- Functional and molecular antibody characterization.

Cell-mediated immune response

- ELISpot IFN γ assay (units: SFU/10⁶ PBMC). An ELISpot assay is used to quantify the amount of peripheral blood mononuclear cells (PBMCs) able to produce IFN γ upon RSV F-protein peptide stimulation.

- Intracellular cytokine staining (ICS, unit: % of subset) or cytokine analysis. Analysis of CD4 and CD8 T-cell subsets and their cytokine expression patterns will be determined by flow cytometry after RSV F-protein peptide stimulation (including, but not limited to CD4/CD8, interleukin-2 [IL-2], IFN γ , TNF α and Th1/Th2 subtyping).

**Cytokine analysis for Th1/Th2 profiling will be done in cases where no ICS data can be generated due to insufficient number of PBMCs for ICS assay (see exploratory endpoints below for description)*

- Cytokine analysis, Cytokine profiles of (in vitro) stimulated PBMC supernatant will be analysed to assess the quantity and quality of the elicited immune responses, including Th1/Th2 balance. Analysis will include, but is not limited to, IFN γ , IL-2, IL-4, IL-5, IL-13, and TNF α , if available.

Immunogenicity against the vector:

- Adenovirus neutralization assay

This assay assesses neutralizing antibody responses against the Ad26 vectors.

